7.5 Method of Assignment/Randomization

Participants will be randomized by family. If the participant will be completing the program and enrolling in the study without parental involvement, they will be randomized individually. Each patient/family will receive a unique study ID at the time of referral to the study that is not connected to identifiable data. Before randomization, the referred patient/family will complete the following enrollment procedures: (1) each referred patient will complete a clinical intake at their referral site with a therapist, (2) each referred patient/ family with complete an assessment to determine eligibility for the study, (3) each referred patient/family will give study staff consent to participate in the study, (4) the participants will complete baseline assessment, and (5) the participants will complete the PARS assessment

Once a participant/family gives consent to enroll in the study, they will be provided with a unique ID number and this ID number will be connected to their identifiable data (access to identifiable data will be limited). The clinical intake can happen before or after consent is received, but the baseline assessment and PARS assessment must be completed after the patient gives consent to enroll in the study. Once all four steps of enrollment (consent, clinical intake, baseline assessment, and PARS) are completed, the participant/family will be randomized.

Anticipated participants were divided into 16 strata based on the 16 combinations of 4 regions (Boston, Miami, Baltimore, Seattle), 2 languages (English, Spanish), and 2 age groups (7-12, 13-18). For each strata, a randomized list of conditions (therapist-led treatment versus guided online treatment) was generated at Sealed Envelope using random blocks of size 4. Random blocks help maintain equally sized treatment groups while also reducing bias in random assignment by making it more difficult for researchers to (deliberately or not) predict the next condition. Random assignment lists have been archived with the Data Management team and with [name].

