Although attempts should be made to collect data from both caregivers and youth across assessment points for all families, to minimize participant burdens and maximize engagement, only caregiver-reports are required to randomize children ages 7-12 years, and only youth self-reports are required to randomize adolescents ages 13-18 years. Furthermore, 7-year-old participants are not to be administered self-report questionnaires, due to concerns about the reliability and validity of self-reports of anxiety in children this age voiced by the trial's patient and family advisory council and scientific advisory panel, and corroborated by scientific literature.¹¹⁶⁻¹¹⁸ Such youth should be administered self-report forms at later assessment points if they turn 8 during the trial. In addition, although youth self-reports of primary and secondary clinical outcomes are to be administered to all youth \geq 8 years, a subset of youth self-report variables will only be administered to youth \geq 13 years given: (a) recommendations from the trial's patient and family advisory council and the scientific advisory panel to minimize the assessment burdens outside of clinical outcomes for participating children \leq 12 years, and (b) concerns from these advisory groups about younger children's abilities to accurately self-report on some of these variables (e.g., their own treatment histories, family treatment barriers; details below).

Measures included in the Kids FACE FEARS trial can be sorted into four groups: (i) Primary Clinical Outcomes. (ii) Secondary Clinical Outcomes; (iii) Treatment Variables; and (iv) Study Covariates, Predictors and Other Included Measures.

7.6.1 Primary clinical outcomes. Primary clinical outcomes assessed in the Kids FACE FEARS trial focused on anxiety symptoms, anxiety-related impairment, treatment responder status, anxiety remission status, and patient-centered outcomes focused on perceived effectiveness and treatment satisfaction. Table 3 presents a summary of the primary clinical outcomes assessed, which are described in detail below.

Table 3. Primary Clinical Outcomes in the Kids FACE FEARS Trial

Domain	Measure	Informant(s)	Assessment Point			
			Baseline	Midtreatment	Posttreatment	1-Year Follow-Up
Youth Anxiety Symptoms	PROMIS Pediatric Short Form-Anxiety (8a v2.0)	C, Y	X	X	X	X
Anxiety-Related Impairment	Child Anxiety Life Interference Scale (CALIS)	C, Y	X	X	X	X
Treatment Responder Status						

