7.15.2 Midtreatment, Posttreatment, and Follow-up Assessment Procedures

Florida International University (FIU) will be responsible for emailing a link to participants to complete the midtreatment, posttreatment, and follow-up assessments. Specifically, all randomized families are invited to complete a midtreatment assessment (consisting of caregiver- and youth self-report questionnaires) once they complete half of their allocated treatment. Families who do not complete half of their allocated treatment by the end of the second month of their treatment phase are invited to complete a midtreatment assessment at Week 8. All randomized families are then invited to complete a posttreatment assessment (consisting of caregiver- and youth self-report questionnaires) once they fully complete their allocated treatment program. Families who do not complete their allocated treatment program by the end of the fifth month of their treatment phase are invited to complete a posttreatment assessment at Week 20. All randomized families are then invited to complete a follow-up assessment at Week 52 (consisting of caregiver- and youth self-report questionnaires). Families will be emailed 2-4 weeks ahead of their follow-up assessment target date (i.e., 2-4 weeks before week 52).

BMC and FIU RAs will assist all sites in conducting follow-up calls to participants in order to increase assessment completion rates. A reminder email will be sent to the participating family by FIU to complete their assessment every 4 days for at least 2 weeks (or until the assessment is complete). FIU RAs will run weekly reports off REDCap to see which participants have not completed their assessments and inform local RAs of which of their participants have outstanding data. If a participant has not completed their assessment after 2 weeks, the RA from the participant's site will call the participant in an attempt to complete the assessment over the phone. For posttreatment assessments, RAs should stop reminder contacts to participants when the participant 8 weeks after the assessment is initially emailed to them. At this point, the posttreatment assessment point is considered missing. For follow-up assessments, RAs should stop reminder contacts to participants 8 weeks after the assessment is initially emailed to them.

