7.15.4 Retention and Study Compensation

Based on similar studies conducted in usual care settings that do not provide free study treatment, we expect roughly 30-50% attrition by the final follow-up timepoint, and roughly 10% of data points to be missing with each collected timepoint. REDCap surveys will be configured to minimize missing values (e.g., requiring participants to complete each item, or explicitly indicate “refuse to answer” before proceeding to the next item; providing real time alerts to the data management team when items or entire forms are missing). Data will additionally be checked on a weekly basis by a research supervisor, and patterns of missingness will be identified and corrected in real time throughout the study. To further reduce instances of missing data, we have kept the number of study forms to a minimum in order to minimize the burden to participants, and participants will be provided compensation for their time completing study forms. Finally, participants will be compensated for the burdens of completing study assessments (see below).

Given the aim to evaluate treatment engagement and performance under typical circumstances, families are not compensated for participating in treatment. To ensure generalizability and observe the treatment comparators under natural conditions, treatment is not funded by the study nor offered for free. Rather, treatment is to be paid for via the natural channels of payment in the participating health centers (e.g., insurance and co-payments). In contrast, families are compensated for participation in study assessments that are not part of the treatment comparators under study. Specifically, families will receive the following compensations for completing various study assessment components:

- a. \$50 for baseline assessment (staggered payments: \$25 following baseline questionnaires and \$25 following baseline PARS completion)
- b. \$25 for midtreatment assessment
- c. \$50 for posttreatment assessment
 - i. \$30 additional compensation for completing posttreatment PARS assessment
- d. \$100 for completing follow-up assessment

*Coaches (who are not guardians) will not receive compensation for the assessments they complete. Compensation will only be provided to the youth and guardian informants. One ClinCard that will be loaded with the above payments will be given to each family for each child enrolled in the study.

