7.16.2 Handling of Missing Data

7.16.2.1 Prevention and monitoring. All study data will be collected via electronic capture and communication directly with the study team. Based on similar studies conducted by our group and in related research in similar settings, we expect roughly 10% of data points to be missing. REDCap surveys will be configured to minimize missing values (e.g., requiring participants to complete each item, or explicitly indicate "refuse to answer" before proceeding to the next item; providing real time alerts to the data management team when items or entire forms are missing). Data will additionally be checked on a weekly basis by a research supervisor, and patterns of missingness will be identified and corrected in real time throughout the study. To further reduce instances of missing data, we have kept the number of study forms to a minimum in order to minimize the burden to participants, and participants will be provided compensation for their time completing study forms. Finally, participants will be compensated for the burdens of completing study assessments at a rate of \$50 for baseline assessments (including PARS) and, \$25 for midtreatment assessments, \$50 for posttreatment assessments (including PARS), \$100 for week 52 assessments and \$30 for completion of PARS at posttreatment (note: compensation will not be provided for completion of measures that will be included as part of routine care). Coaches will not receive compensation for the assessments they complete.

7.16.2.2 Statistical handling of missing data. All analyses will consist of intention-to-treat models drawing on all available data. To account for missing data, we will employ multiple imputation. Recommended procedures for single and multilevel multiple imputation will be conducted using BLIMP software, using fully conditional specification multiple imputation (FCS-MI). For each model, 50 datasets with imputed values will be created using other model covariates as predictors of missingness. Model convergence will be assessed across 8 Markov Chain Monte Carlo (MCM) processes and verified for potential scale reduction (PSR) factor<1.05. Main analyses will be conducted on the imputed dataset and the results will be pulled for final estimates (using R 4.4.1 mitml for imputation pooling per Rubin's rules, and lme4 for multilevel models, or lm and glm for linear and logistic regression models).

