7.16.3 Covariates

Covariates for each model will include site, language of care, youth age, youth gender, youth race, youth ethnicity, and family resource insecurity (see Measures)

7.16.4 Primary analyses: Comparative effectiveness analyses. For primary analyses on continuous outcomes that were measured across the 4 major timepoints (e.g., caregiver- and youth-reports on the PROMIS Anxiety Scale, CALIS), mixed models of change¹⁴⁴ will be run separately for each outcome. Mixed models are preferred for longitudinal designs because they allow for individual estimates of change and have robust power in the presence of missing data and attrition.^{145,146} Covariates for each model will include site, language of care, youth age, youth gender, youth race, youth ethnicity, and family resource insecurity (see Measures), and any other baseline variables found to significantly differ across participants in the two conditions. The random effects of intercept (reflecting individual variation in mean outcome level) will be assessed. The fixed effects of Treatment Condition, Time, and the Treatment \times Time interaction will be analyzed in the prediction of change. We will examine non-linear models of change (i.e., log transformations of Time), which afford examination of symptom trajectories across time that are not gradual and incremental (e.g., steep improvements during initial weeks of treatment, followed by a slowing down of improvements toward the end of treatment, and then relative stability across the follow-up time interval). To aid interpretation of the meaningfulness of between-group differences, Cohen's d 's will be computed for each continuous outcome on model means at post and follow-up.

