For primary analyses on the dichotomous categorical outcomes PARS Treatment Responder Status at posttreatment, baseline PARS scores will be examined for each participant to determine their individual thresholds for classification as Treatment Responders (i.e., 35% PARS score reduction). These thresholds will be used to classify each participant's statuses as posttreatment. Logistic regression models will examine Treatment Condition (along with the study covariates) as a predictor of Treatment Responder Status and Remission Status at post. For primary analyses on continuous outcomes of Treatment Satisfaction at post, linear regression models will examine Treatment Condition (with the study covariates) as a predictor of caregiver- and youth-reported posttreatment satisfaction.

7.16.5 Heterogeneity of treatment effects. For Aim II analyses (heterogeneity of treatment effects) predictor and moderator terms will be added to the models predicting youth anxiety severity that were outlined above. For study covariates being considered as predictors/moderators (e.g., language of care, youth age, youth gender, youth race, youth ethnicity, and family resource security), this will entail only adding interaction terms, as the main effects of these variables will already be in the models. For the additional variables considered as treatment moderators that are not already included as model covariates (e.g., caregiver nativity) this will entail adding main effects and interaction terms to the models. For each model examining heterogeneity of treatment effects, the relevant terms of interest will be the 2-way interaction of Variable \times Time (reflecting whether the variable uniformly predicted change across the two treatments) and the 3-way interaction of Variable \times Treatment Condition \times Time (reflecting whether the variable moderated treatment effects; i.e., whether the variable predicted differential response across the treatments). As with the Aim I comparative effectiveness analyses, log transformations of Time will be entered to consider non-linear models of change. Significant interactions will be followed up with post-hoc probing on subgroups to clarify the nature and direction of interaction, and results will be plotted for visual depiction.

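### Missing PARS responder status would be imputed only from the responder model's own covariates, which adds almost nothing to a complete-case analysis

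*Combined protocol and SAP*

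**What the plan says.** Section 7.16.2.2 gives one general imputation rule: "For each model, 50 datasets with imputed values will be created using other model covariates as predictors of missingness". Section 7.16.3 lists the covariates: site, language, age, gender, race, ethnicity and resource insecurity. Section 7.16.4 then gives the responder analysis: "Logistic regression models will examine Treatment Condition (along with the study covariates) as a predictor of Treatment Responder Status and Remission Status at post".

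Baseline PARS has one role in that analysis: "baseline PARS scores will be examined for each participant to determine their individual thresholds for classification as Treatment Responders". It should be available for every randomized child, because section 7.5 states: "Once all four steps of enrollment (consent, clinical intake, baseline assessment, and PARS) are completed, the participant/family will be randomized". Table 3 schedules PROMIS and CALIS at all four assessment points, but in the analysis sections they appear only as outcomes of their own mixed models.

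On losses, section 7.15.4 expects "roughly 10% of data points to be missing with each collected timepoint" and 30-50% attrition by the final follow-up.

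**The concern.** No sentence sets out an imputation model for PARS, but the general rule implies one: arm plus the seven covariates. None of these measures anxiety. PARS is taken only at baseline and posttreatment, so the responder model cannot borrow from other visits as the mixed models for PROMIS and CALIS can. The plan also does not say whether the posttreatment score or the binary status is imputed. The same applies to Remission Status, for which the plan gives no definition.

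The useful information is often likely to be there. Posttreatment questionnaires are sent by email (7.15.2). The PARS interview needs a central assessor (7.15.3) and carries its own payment (7.15.4). Questionnaires can therefore be present when PARS is missing.

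PARS supplies the primary outcomes rated by masked evaluators, although from interviews with families who know their arm. If loss of PARS depends on symptoms and its rate or strength differs by arm, the planned estimate is biased and the planned imputation does not help. The documents give some ground for unequal rates: the background section warns of high attrition in self-administered online care. They give no ground for dependence in one arm only.

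**Working it through.** **1. What the stated rule does.** Suppose only the outcome is missing. The imputation model for status given arm and covariates is then the analysis model itself, fitted to the observed cases. Values drawn from it return the same coefficients apart from simulation noise. Two simulations confirm this:

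- 150 per arm, 20% missing, dropout tied to non-improvement in one arm, auxiliary correlation 0.5: log-odds ratio 0.427 imputed, 0.424 complete-case, 0.615 with full data; standard errors 0.269 and 0.268.
- With the study covariates entered as 11 terms (500 replicates), the planned method matched complete cases within 0.003 on the log-odds ratio.

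**2. Size of the bias, algebra.** Leave covariates aside. In an arm with missing fraction m, the true rate is (1 − m)·p_obs + m·p_mis, while the planned method reports p_obs. The error is m·Δ, where Δ = p_obs − p_mis. The error in the gap (more effective minus less effective arm) is m_E·Δ_E − m_L·Δ_L. It vanishes when m and Δ are alike in both arms.

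**3. Size of the bias, simulation.** The plan gives no responder rates and no missing-PARS rate by arm, so all inputs are assumed.

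- Baseline PARS: mean 15, SD 5, limited to 5-30.
- Shift model: posttreatment SD 5.5, correlation 0.4, 2-point difference; true rates 42.1% vs 57.5%, gap 15.4 points, log-odds ratio 0.62.
- Mixture model: 42% vs 60% latent responders fall 55% (SD 12), others 8% (SD 15); true rates 42.0% vs 58.5%, gap 16.4 points before rounding, log-odds ratio 0.66.
- Six caregiver scores (PROMIS and CALIS at three visits); posttreatment correlation with PARS 0.6 and 0.5.
- Log-odds of missing PARS rise by 0.5 or 1 per SD of posttreatment PROMIS.
- 600,000 per arm for bias.

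Planned gap in points (shift / mixture), with the same dependence in both arms:

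| Missing, less vs more effective arm | Slope 0.5 | Slope 1 |
|---|---|---|
| 15% vs 5% | 14.5 / 15.5 | 13.8 / 14.9 |
| 20% vs 10% | 14.5 / 15.6 | 14.0 / 14.9 |
| 30% vs 10% | 13.6 / 14.6 | 12.3 / 13.4 |
| 5% vs 15% | 16.3 / 17.4 | 17.1 / 18.3 |
| 10% vs 20% | 16.3 / 17.5 | 17.1 / 18.2 |
| 10% vs 30% | 17.2 / 18.4 | 18.7 / 19.7 |

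With equal rates and dependence the gaps are 15.4 and 16.5, so no bias. The algebra agrees. For slope 1 under the shift model at 15% vs 5%, the error is 13.8 − 15.4 = −1.6 = (0.05 − 0.15)·Δ, so Δ is 16 points. At 30% vs 10%, −3.1 = (0.10 − 0.30)·Δ gives 15.5 points.

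Stress case, slope 1 in one arm only, equal rates of 10/20/30%: 13.7/12.0/10.5 (shift) and 14.6/13.0/11.4 (mixture) when the less effective arm is affected; 17.1/18.8/20.3 and 18.4/20.1/21.6 when the more effective arm is.

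**4. False positives** (150 per arm, 1,500 replicates, 20 imputations, Rubin's rules). At 10% missing overall the rate stays at 5-7%. With equal dependence, slope 1, 30% vs 10%, it is 7-9%. In the one-arm stress case at 10/20/30% it is 6.1/8.6/11.9% (shift) and 5.5/8.7/13.3% (mixture).

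**5. With the auxiliaries.** Imputing status from arm, covariates, baseline PARS and the six scores comes within 0.3 points of the truth when posttreatment questionnaires are present. It removes about 55-75% of the bias when half of those missing PARS also lack questionnaires. The one-arm false-positive rate falls to 4-6%, or 4-7% with half lacking. With the 11 covariate terms, one arm at 30% (shift / mixture), the log-odds ratios are: full data 0.642 / 0.706, planned 0.445 / 0.510, six scores 0.633 / 0.697, twelve scores (caregiver and youth) 0.630 / 0.693.

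If PARS itself drives missingness, only about 25-40% of the bias is removed (15-30% with half lacking questionnaires). At slope 1 and 15% vs 5%, the planned gaps are 12.8 / 13.9 and the proposed 13.8 / 14.9: under the shift model, 1.0 of a 2.6-point error.

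**The case against.** **The restriction is inferred.** The plan never excludes auxiliary variables and refers to recommended procedures. That is true, but 7.16.2.2 does name the predictors, and its plain reading with 7.16.3 and 7.16.4 leaves the anxiety measures out. If the score is imputed and then classified, baseline PARS enters the classification, but still not the prediction of the missing score.

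**Baseline PARS might enter another way.** Section 7.16.4 also adds baseline variables that differ significantly between arms. That clause is written for the mixed models and depends on the data, and it could never admit midtreatment or posttreatment scores.

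**The effect is small at the plan's own rate.** This stands. At about 10% missing the error is 1-2 points. The 30% rows exceed both that figure and a straight-line reading of the attrition range back to Week 20 (30% × 20/52 = 11.5%; 50% × 20/52 = 19.2%). Families who leave treatment are still sent all assessments (7.16.2.4), and check-in calls are meant to hold online attrition down.

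**The benefit is partly built in.** This also stands. The main simulation ties missingness to posttreatment PROMIS, which the fix includes. The weaker results when PARS itself drives missingness are the fairer lower bound.

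**Adding baseline PARS to the logistic model is a separate choice.** Agreed; it does not repair the imputation.

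**Conclusion.** The point holds. As worded, multiple imputation of Responder Status is in effect a complete-case analysis whenever only the outcome is missing. The consequence is modest at the expected 10% missing and nil if data are missing completely at random or if loss works alike in both arms. It reaches about 2-3 points of a 15-16 point gap at 30% vs 10% missing with the same symptom dependence in both arms, and about 5 points in the one-arm stress case at 30%. The estimated gap shrinks if the excess or symptom-related loss is in the less effective arm and grows if it is in the more effective one. All these sizes rest on assumed rates, correlations and missingness mechanisms. This is a change the plan should make because the data are already scheduled and the remedy is cheap; it does not undermine the trial.

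**What to change.** In 7.16.2.2, state what is imputed for PARS and fix a short auxiliary list before analysis: arm, the study covariates, baseline PARS, and PROMIS and CALIS at baseline, midtreatment and posttreatment (caregiver report, plus youth report where age allows). Attendance is optional. Impute Responder Status directly from this list. As a check, impute the posttreatment PARS Total from the same list and derive status. Also add baseline PARS as a covariate in the logistic model; this last step can be decided separately.

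The cost is SAP wording and modest programming, with no new data and no change of outcome.

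- The auxiliaries have gaps of their own, which the imputation must fill: "only caregiver-reports are required to randomize children ages 7-12 years, and only youth self-reports are required to randomize adolescents ages 13-18 years", and 7-year-olds give no self-report.
- The linear score imputation used as the check lost 0.4/0.8/1.2 points at 10/20/30% missing completely at random under the mixture model, and nothing under the shift model.
- Adding baseline PARS to the logistic model moved the log-odds ratio from 0.620 to 0.635 under the shift model and not at all under the mixture, and changed power by −1 to +2 points.
- If data are missing completely at random, the auxiliaries gain only 1-2 points of power at 10% missing and 4-5 at 30%.
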